8.3. Subgroup Analyses

For period 1, the clinical subgroup of interest are

- Sjögren patients
- Subjects who experienced marked improvement during Period 1 where marked improvement is defined as CFS score improvement from baseline of 2 grades or more on the modified Oxford scale [unless if the patient had a CFS score of 5 at baseline, the improvement in CFS has to be 3 grades or more] in the analysis eye.

Efficacy analysis of Period 1 will be repeated using this subpopulation.

For Period 2, subgroup analysis by Sjögren patients will be conducted to investigate the treatment effects of the target population across region in Period 2. Other subgroup analyses may be performed as deemed necessary.

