### 7. SELECTION AND WITHDRAWAL OF SUBJECTS

## 7.1. Subject Inclusion Criteria

Patient eligibility is determined according to the following criteria:

- 1. In the opinion of the investigator, the patient is capable of understanding and complying with protocol requirements.
- 2. The patient has signed and dated a written informed consent form and any required privacy authorization prior to the initiation of any study procedures.
- 3. Male or female patient is aged 18 years or above.
- 4. At least 4 weeks of use of tear substitutes prior to the Baseline Visit
- 5. DED patients with severe keratitis defined as the following:
  - CFS score of 3, 4 or 5 on the modified Oxford scale in at least one eye at Baseline Visits,

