3.3. Sample Size Determination

The sample size of this study is not planned from a formal sample size calculation since formal statistical hypothesis testing will not be performed for the primary endpoints. In this study, we plan to enroll 350 subjects. Of the 350 subjects, it is estimated that approximately 70% (245 subjects) would become markedly improved in CFS after Month 12 and enter the Period 2 (double-masked randomized period), based on Santen previous IKERVIS studies. With a 3:2 randomization allocation ratio, a sample size of 147 for IKERVIS® and 98 for Vehicle will allow us to detect a difference of 0.4 or more in CFS score with 80% power assuming the standard deviation of the difference is 1.10.

Petroutsos *et al.* (1992) showed that after 6 years of follow-up on DED subjects, a lower-bound of the estimated complication rate was 4% in severe DED subjects. In the current study, 350 subjects treated with IKERVIS® for at least one year would have 95% power to detect at least one ocular complication that occurs at 1% rate with type I error rate of 0.05.

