- The Sjögren Patients Population (Period 2 or Entire Study) consists of subjects who were known to have diagnostic status of the Sjögren disease based on the medical history obtained at baseline and satisfies FAS Period 2 or Safety Population Period2 criteria depending on analysis.

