8. EFFICACY ANALYSES

Unless otherwise specified, all efficacy analyses will be performed on the study eyes of the FAS Period 1 population, the Sjögren Patients in Period 1, the Subjects Markedly Improved in Period 1, the FAS Period 2 population, the FAS Entire Study population, and Sjögren Patients to satisfy FAS Period 2 (or FAS Entire Study Population).

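### The Period 2 Sjögren analysis in SAP 8.3 has no non-Sjögren comparator and no treatment-by-Sjögren contrast, so it cannot show whether the treatment effect differs by Sjögren status

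*SAP*

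**What the plan says.** SAP 8.3 (Subgroup Analyses) says that for Period 2 "subgroup analysis by Sjögren patients will be conducted to investigate the treatment effects of the target population across region in Period 2". SAP 8 (Efficacy Analyses) lists the sets used for all efficacy analyses unless otherwise specified; the list ends with "the FAS Entire Study population, and Sjögren Patients to satisfy FAS Period 2 (or FAS Entire Study Population").

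SAP 6 (Analysis Population) defines the Sjögren set as one that "consists of subjects who were known to have diagnostic status of the Sjögren disease based on the medical history obtained at baseline", restricted for Period 2 to patients who also meet the FAS or safety criteria. It defines no complementary non-Sjögren set.

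The MMRM in SAP 8.2.1 contains treatment, visit, treatment by visit, the Month 12 value and region. The Cox model for relapse in SAP 8.2.3 contains treatment, region and Month 12 CFS. Neither has a Sjögren term. The MMRM reports a nominal p-value at each visit and names the Period 2 FAS as its population.

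Eligibility in Protocol 7.1, criterion 5, is "DED patients with severe keratitis defined as the following": a CFS grade, a Schirmer value and symptom scores. Sjögren disease is not among the criteria.

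Protocol 13.4 plans one homogeneity analysis of Period 2 treatment effects, by the randomisation stratification factor, which SAP 3.2 gives as region. SAP 8.3 does not carry it over, and SAP 10 does not list its removal. The heading of Protocol 13.3 and the synopsis say only that Sjögren patients will be described separately for some analyses.

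**The concern.** Whether IKERVIS works differently in Sjögren patients is a question about the difference between two treatment effects. An analysis confined to one subgroup gives one of those effects and nothing to set it against.

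The subgroup is smaller than the full set, so an inconclusive Sjögren result is likely even if the treatment works equally well in everyone. With the patients labelled as the target population, that result could be read as absence of benefit where benefit was most wanted. A favourable Sjögren result could equally be read as specific to Sjögren disease when the remaining patients would show the same.

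The phrase 'across region' adds uncertainty. It may be left over from the protocol's homogeneity analysis by region, or it may mean something else.

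**Working it through.** **Inputs.** From SAP 3.3: "a sample size of 147 for IKERVIS® and 98 for Vehicle", able to "detect a difference of 0.4 or more in CFS score with 80% power", "assuming the standard deviation of the difference is 1.10". The 0.05 error rate there ("with type I error rate of 0.05") is stated only for the complication calculation, so a two-sided 5% test for CFS is an assumption. The Sjögren share *f* is not given; 20%, 30% and 40% are assumed, with 10% and 50% as a wider check. Further assumptions are one visit, no dropout, the same SD in both subgroups, and a 3:2 split inside each subgroup (Sjögren status is not a stratum, so the actual split may differ).

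**Step 1: the plan's own figure.**
SE = 1.10 × √(1/147 + 1/98) = 0.1435.
0.4 / 0.1435 = 2.79.
Power ≈ Φ(2.79 − 1.96) = 79.6% (noncentral t: 79.3%). The stated 80% reproduces.

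**Step 2: power in each subgroup when the true difference is 0.4 in everyone.**
SE_S = 0.1435/√f and SE_N = 0.1435/√(1 − f). Power ≈ Φ(0.4/SE − 1.96); the opposite tail is negligible.

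| f | Sjögren n (IKERVIS : Vehicle) | SE_S | Power, Sjögren | SE_N | Power, non-Sjögren |
|---|---|---|---|---|---|
| 20% | 49 (29 : 20) | 0.321 | 24% | 0.160 | 70% |
| 30% | 74 (44 : 29) | 0.262 | 33% | 0.171 | 65% |
| 40% | 98 (59 : 39) | 0.227 | 42% | 0.185 | 58% |

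Allocations are rounded separately. Noncentral t lowers the Sjögren power by less than one point (to 23% at f = 20%).

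**Step 3: how often the subgroups disagree on significance although their true effects are identical.**
P(disagree) = P_S(1 − P_N) + P_N(1 − P_S).
For f = 20%: 0.239 × 0.297 + 0.703 × 0.761 = 0.071 + 0.535 ≈ 61%. For 30%: 55%. For 40%: 51%.

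**Step 4: precision of the contrast that is missing.**
SE_I = √(SE_S² + SE_N²) = 0.359, 0.313, 0.293. The 95% half-width, 1.96 × SE_I, is 0.70, 0.61 and 0.57 CFS grades. Power to detect a 0.4-grade difference between the subgroup effects is 20%, 25% and 28%. The difference detectable with 80% power is 1.00, 0.88 and 0.82 grades.

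**Wider range of f.** At 10% and 50%, power in the Sjögren set is about 14% and 50%, and disagreement 68% and 50%. The conclusion does not depend on the exact share.

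**The case against.** **The plan is exploratory.** SAP 5.4 says so and plans no multiple-comparison procedure. Protocol 13.1.2 states that there are no hypotheses for the primary and secondary endpoints. The MMRM p-value is called nominal. This stands. A reader might infer that the Sjögren analysis opens a second route to a treatment claim and inflates a 5% error rate. The documents do not support that, because no controlled claim on the full set exists to be inflated.

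**No document states that a p-value will be computed in Sjögren patients.** SAP 8.2.1 names the Period 2 FAS for the MMRM, the relapse and complete-resolution analyses do likewise, and the sentence in SAP 8.3 about repeating the efficacy analysis is written for Period 1. This also stands. Use of the MMRM and its p-values in the subgroup is inferred from the list in SAP 8 and from the reference to treatment effects in SAP 8.3. No rule says that a conclusion will be drawn from such a p-value. The missing comparator and contrast do not depend on the inference.

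**The sentence may mean by Sjögren status.** SAP 7.2 does summarise status as yes or no. But SAP 6, 7 and 8 define and use only the positive set; if status is meant, the text should say so.

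**Interest in Sjögren patients is legitimate.** The protocol's introduction places them among those with a worse prognosis, and they are mentioned in advance. That justifies looking at them. It does not make them the trial's target population, and it does not supply the comparison.

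**Low power is a property of any small subgroup.** True, and the interaction estimate will be imprecise too. That is a reason to report an estimate with its interval instead of a pass/fail test.

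**Conclusion.** The point holds as a gap in an exploratory plan that invites misinterpretation. SAP 8.3 sets out to investigate Period 2 treatment effects in Sjögren patients alone, under a label that eligibility does not support. Nothing planned in either document would show whether the effect differs by Sjögren status. No primary endpoint or confirmatory test depends on it.

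The numerical size rests on an assumed Sjögren share and on the single-visit, no-dropout simplification; the SD, the difference and the group sizes are the plan's own. Under those assumptions, significance or its absence in the Sjögren set says little about heterogeneity.

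**What to change.** In SAP 8.3, replace the Period 2 sentence with:

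> Treatment effect by Sjögren status (yes/no) in Period 2 will be estimated by adding Sjögren status, Sjögren-by-visit, treatment-by-Sjögren and treatment-by-Sjögren-by-visit terms to the CFS and SANDE MMRMs. The IKERVIS-Vehicle difference with 95% CI will be reported for Sjögren and non-Sjögren patients, with the difference between them and its 95% CI. This is exploratory; no conclusion will rest on a p-value within one subgroup, and a non-significant interaction will not be read as homogeneity.

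This removes the 'target population' wording. Resolve 'across region' by either restoring the Protocol 13.4 homogeneity analysis by stratification factor or listing its removal in SAP 10.

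The cost is SAP wording and a few model terms, since Sjögren status is already collected at baseline. The downside is an imprecise estimate of the difference between subgroups. The text covers CFS and SANDE only; any other endpoint for which a Sjögren comparison is wanted needs the same treatment.

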9. SAFETY ANALYSES

The safety-related measures collected in this study include AEs, intraocular pressure (IOP), best-corrected distance visual acuity (BCDVA), and slit-lamp biomicroscopy. All the safety-related measures will be summarized descriptively on the Safety population by study period and by actual treatment received (Period 2).

9.1. Analysis of Primary Safety Endpoint

The primary safety endpoint for this study is the incidence rate and time-to-onset of ocular surface complications, which include corneal ulceration, corneal perforation, loss of visual acuity, or ocular infection. Missing data will not be imputed.

The ocular surface complications incidence rate will be tabulated using frequency (n) and percentage (%) at Month 1-12, Month 13-24, Month 25-36 and for overall period 2 (Month 13-36). Month 1-12 incidence rate will be summarized for Period 1 Safety population. Month 13-

24, Month 25-36, and Month 13-36 (overall period 2) summaries will be conducted for Period 2 Safety population. The relative risk of the ocular surface complications incidence rate between the two treatment groups will be assessed at Month 13-24, Month 25-36 and Month 13-36 by producing odds ratio and its 2-sided 95% exact confidence interval.

For entire study analysis, the ocular surface complications incidence rate of IKERVIS group (a treatment group with IKERVIS during period) at Month 36 (1-36) will be compared to the existing epidemiologic rate in a comparable population, which was 4% based on results published by Petroutsos *et al.* (1992). The ocular surface complications incidence rate at Month 36 will be compared. This will be done using the Safety population Entire Study. Binomial proportions will be compared using SAS procedure PROC FREQ with binomial options.

The relative risk of the two treatment groups in terms of the time-to-first-onset of ocular surface complications (first event of each subject) will be assessed by producing the hazard ratio and its 2-sided 95% confidence interval if enough events are observed to make the analysis possible for period 2 (double masked period). The estimated hazard ratio and 95% CI will be obtained from a Cox proportional hazards model with treatment group as a covariate and region as stratification factor. Survival functions will be estimated using the Kaplan-Meier method, and Log-Rank test will be conducted to calculate nominal p-value.

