### Analysis of Primary Efficacy and Safety Endpoints

Spearman correlation coefficient will be obtained between mean change from baseline in CFS score at visit X and SANDE symptoms score at each visit X+i for each FAS population in Period 1, Period 2, and entire study. For Period 1, visit X includes Day1, Month 3, Month 6, Month 9 and Month 12, and i is from 0 (Day 1) up to 4 (Month 12). For Period 2, X includes Month 12, Month 15, Month 18, Month 21, Month 24, Month 27, Month 30, Month 33, and Month 36, and i is from 0 (Month 12) up to 8 (Month 36). Correlation coefficient will be analized by treatment group. For entire study, visit X includes all the scheduled visits from Day 1 to Month 36, and i is from 0 (Day1) up to 12 (Month 36). Missing data will not be imputed.

The incident rate of ocular surface complications (defined as corneal ulceration, corneal perforation, loss of visual acuity, and ocular infection) will be estimated with its 95% CI for each safety population in Period 1, Period 2, and the entire study. The analysis for safety population in Period 2 will be conducted by treatment group. These rates will be compared to existing epidemiologic rates in a comparable population. Time to onset and time to resolution of the ocular complications will also be summarized.

Missing data will not be imputed.

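### SAP 9.1 drops the protocol's per-group 95% CI from the complication rates, and its later-interval percentages and odds ratios take no account of patients who have already left

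*SAP*

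**What the plan says.** **Protocol.** The synopsis says that the complication rate "will be estimated with its 95% CI for each safety population in Period 1, Period 2, and the entire study", with Period 2 split by treatment group. Section 13.4 repeats the CI requirement but names only Period 2 (by treatment group) and the entire study.

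**SAP 9.1.** The rate "will be tabulated using frequency (n) and percentage" for Month 1-12, Month 13-24, Month 25-36 and Month 13-36. The first interval uses the Period 1 Safety population. For the others, "Month 13-36 (overall period 2) summaries will be conducted for Period 2 Safety population" (Month 13-24 and Month 25-36 are named in the same sentence). The arms are compared in each Period 2 interval by an odds ratio with an exact 95% CI. Time to first complication in Period 2 gets Kaplan-Meier curves, a log-rank test and, if there are enough events, a Cox hazard ratio with 95% CI. The entire-study IKERVIS rate is compared with 4% by a binomial procedure.

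**SAP section 6.** The Period 2 Safety population requires randomisation, one masked dose and any Period 2 follow-up.

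**SAP section 10.** The list of changes to the protocol's analyses does not mention the missing CI.

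**The concern.** There are two separate matters.

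1. **Precision.** Few events are expected; the SAP itself makes the Cox model conditional on having enough of them. With few events the width of the interval carries most of the information about a single arm's rate, and n and % do not show it. The odds ratio and hazard ratio intervals describe the contrast between arms, not the rate in either arm, and neither exists for the single-arm Period 1.

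2. **Denominator.** If the Month 25-36 percentage is taken over the whole Period 2 Safety population, a patient who left at Month 15 counts as event-free in a year when nobody was observing that patient. The same happens, less sharply, within Month 13-36. The percentage then falls below the risk among those followed, and the odds ratio mixes complication risk with retention.

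The plan allows for early exits: SAP 7.7 has Period 2 exposure categories from 1-90 days, SAP 7.1 tabulates Month 36 non-completers with reasons, and Protocol 7.5 says leavers are not replaced.

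**Working it through.** **Arm sizes.** SAP 3.3 says that "a sample size of 147 for IKERVIS® and 98 for Vehicle will allow us to detect a difference of 0.4 or more in CFS score". The claimed power is 80% and the SD is taken as 1.10. No alpha is given for this figure; I assume two-sided 0.05.

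- Standard error = 1.10 x sqrt(1/147 + 1/98) = 1.10 x 0.1304 = 0.1435.
- 0.4 / 0.1435 = 2.79; 2.79 - 1.96 = 0.83; power = 79.6%.

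This reproduces the stated 80%, so 147 and 98 are used below. No stated figure is in dispute here.

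**Missing intervals.** Exact (Clopper-Pearson) 95% limits for illustrative counts:

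| Events / patients | % | 95% CI |
|---|---|---|
| 0/147 | 0 | 0 to 2.5 |
| 0/98 | 0 | 0 to 3.7 |
| 4/147 | 2.7 | 0.7 to 6.8 |
| 4/98 | 4.1 | 1.1 to 10.1 |
| 3/350 (Period 1) | 0.9 | 0.2 to 2.5 |

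**Month 25-36 percentage.** Let r be the year-3 risk among those still in the study at Month 24 and d the share gone before then. On the whole set, the percentage = r x (1 - d). The values of d and r are assumptions.

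| d | r = 4% shows as | r = 2% shows as |
|---|---|---|
| 0% | 4.0% | 2.0% |
| 10% | 3.6% | 1.8% |
| 20% | 3.2% | 1.6% |
| 30% | 2.8% | 1.4% |
| 40% | 2.4% | 1.2% |

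**Month 25-36 odds ratio (IKERVIS to vehicle), true risk 4% in both arms.**

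- Equal loss: 1.00.
- Loss 10% IKERVIS, 30% vehicle: (0.036/0.964) / (0.028/0.972) = 1.30.
- Loss 30% IKERVIS, 10% vehicle: the inverse, 0.77.
- Loss 20% IKERVIS, 40% vehicle: (0.032/0.968) / (0.024/0.976) = 1.34.

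**Month 13-36.** Assume a true two-year risk of 4% with constant hazard h = -ln(0.96)/2 = 0.0204 per year, and constant drop-out hazard L = -ln(1 - d) per year, so that d have left by Month 24. Observed percentage = h/(h + L) x (1 - exp(-2(h + L))).

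- d = 10% (L = 0.105): 3.6%.
- d = 30% (L = 0.357): 2.9%.
- Ratio 1.26 where the truth is 1.00.

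**The case against.** **The arms are compared by better methods elsewhere.** A reader might infer from the crude tables that the arms cannot be compared for complications at all. The documents do not support that. SAP 9.1 plans Kaplan-Meier, log-rank and, if feasible, Cox for Period 2, and time to onset is itself part of the primary safety endpoint. These handle unequal follow-up under non-informative censoring. This stands, and it confines the point to the crude percentages and odds ratios. It does not remove it: no Kaplan-Meier estimate or CI at a stated month is specified, and the odds ratio is the only between-arm estimate with a CI that is planned unconditionally.

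**The denominator is inferred.** SAP 9.1 names the analysis set and never writes out the divisor. That stands as a caution, although a programmer following the text would divide by the whole set.

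**Size and direction are unknown.** A reader might infer that year-3 risk will be understated, or that vehicle will look safer than it is. Neither follows, because there is no drop-out figure. Lack of efficacy is a listed withdrawal reason and could remove more vehicle patients; instillation site pain was more frequent on IKERVIS in the pivotal trial (29.2% against 8.9%, Protocol 4.1.1) and could act the other way. Nor is 4% an annual risk in the documents: it is a lower bound after six years of follow-up, used above only as an illustration.

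**The distortion is small beside chance.** With 10% and 30% loss and a true 4%, expected year-3 events are 147 x 0.036 = 5.3 and 98 x 0.028 = 2.7. The nearest whole counts, 5/147 and 3/98, give an exact 95% CI for the odds ratio of 0.21 to 7.3. This stands for the odds ratio. It also shows why each arm's rate needs its own interval.

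**Intervals are not absent altogether.** The odds ratio and hazard ratio have them, and the binomial procedure would probably print one for the entire-study rate. The gap is in the single-group interval rates. For Month 1-12 the requirement rests on the synopsis alone.

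**Conclusion.** The missing CI is established from the text: the protocol requires it, SAP 9.1 leaves it out for every interval rate, and section 10 does not say so. On a primary endpoint that should be corrected.

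The denominator problem follows from the SAP read as written. Its size depends on assumed drop-out: the Month 25-36 percentage falls short of the risk among those followed by 0-40% in relative terms when 0-40% have left before Month 24, and by nothing if nobody has. The odds ratio is distorted only if drop-out differs between arms, and then in either direction. The planned time-to-event analyses for Period 2 are not affected in this way. This is a correction that should be made; it does not invalidate the safety analysis.

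**What to change.** 1. Add an exact 95% CI to every single-group complication rate: Month 1-12, and Month 13-24, 25-36 and 13-36 by arm. State the CI explicitly for the entire-study rate too.
2. Report events per 100 patient-years by interval and arm with exact Poisson 95% CIs, using the treatment dates defined in SAP 4.1.2 and the visit dates.
3. Read the planned Period 2 Kaplan-Meier curves, with time zero at Month 12, at Months 24 and 36 by arm with 95% CIs. Do not run one curve across Month 12: patients who are not markedly improved are withdrawn there, so censoring would depend on response.
4. Keep the crude percentages as a supporting display, with the divisor written out and the number under observation at the start of each interval alongside. Restricting the divisor to those still observed would not by itself restore the randomised comparison, because staying in the study is a post-randomisation event.
5. Record any remaining departure from Protocol 13.4 in SAP section 10.

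The cost is SAP wording and a few more table columns. No new data are needed. Items 2 and 3 still assume that leaving is unrelated to complication risk, and the SAP should say so.
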